  TIME time*event(0);
  TEST trtGroup;
RUN;
```

Other code may be needed to analyze the difference in event rates between arms.

Explanation of variables

- trtGroup (treatment group):
 - Equals 1 if subject randomized to the treatment arm
 - Equals 0 if subject randomized to the control arm
- Event
 - Equals 1 if subject experienced a component of the primary safety endpoint during follow-up on or before the 6-month visit
 - Equals 0 if a subject did not experience a component of the primary safety endpoint during follow-up on or before the 6-month visit
- Time (from procedure date to first event or censor in days)
 - If Event = 1

- Determine the earliest date that a component of the primary safety endpoint was experienced for each subject
 - If the earliest event onset date is equal to a follow-up visit date within the 6-month visit window, then Time equals 180 days
 - If the earliest event onset date is prior to the subjects 6-month visit window, then Time equals the earliest date that a component of the primary safety endpoint was experienced minus the date of procedure
- If Event = 0 (censor)
 - and the 6-month follow-up visit was completed within the 6-month visit window, then Time equals 180 days
 - and the 6-month follow-up visit was not completed, then Time equals the date of the latest visit prior to the 6-month visit minus the date of procedure

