7.10.7.4. Analysis Methods

A logistic regression model will be used with presence of each symptom at 6 months as the response and study arm indicator and baseline presence of symptom as covariates. An alpha of 0.05 will be used to

determine the significance of each covariate. Odds ratios and their corresponding 95% confidence intervals will be reported for each covariate to characterize their estimated effect on the response.

Code similar to the following can be used for the logistic regression models:

```
PROC LOGISTIC DATA = Data;
  CLASS trtGroup;
  MODEL Endpoint = trtGroup symptom_at_baseline / expb;
  RUN;
```

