7.10.7.6. Subgroup Analyses

The subgroups to be analyzed are defined in section 7.9. A logistic regression model will be constructed each subgroup. The model will include covariates for subgroup and the interaction between subgroup and treatment.

Code similar to the following can be used for the logistic regression models:

```
PROC LOGISTIC DATA = Data;
  CLASS trtGroup subgroup;
  MODEL Endpoint = trtGroup symptom_at_baseline subgroup
    trtGroup*subgroup / expb;
  RUN;
```

7.10.8. Ancillary #5: Freedom from chronic treatment failure and off Class I and III anti-arrhythmic drugs following the blanking period

Compare the rate of chronic treatment success (primary effectiveness endpoint) between study arms for subjects off of Class I and III anti-arrhythmic drugs following the blanking period.

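### The sample logistic code for the symptoms objective (SAP 7.10.7.4 and 7.10.7.6) does not match its text: under 1/0 coding it inverts the baseline-symptom odds ratio and gives no usable arm odds ratio in the subgroup model

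*SAP*

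**What the plan says.** Ancillary objective #4 compares symptoms at 6 months between arms. SAP 7.10.7.4 specifies a logistic regression with "presence of each symptom at 6 months as the response", and with arm and baseline presence of the symptom as covariates. Protocol 12.6 describes the same model. The SAP then says what is to be reported: "Odds ratios and their corresponding 95% confidence intervals will be reported for each covariate".

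The sample code is introduced with "Code similar to the following can be used for the logistic regression models". Its class statement is "CLASS trtGroup" and its model statement is "MODEL Endpoint = trtGroup symptom_at_baseline / expb". There is no event option on the response and no parameterisation or reference option on the class variable. Baseline symptom is not a class variable.

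SAP 7.10.7.6 repeats the pattern for the subgroup model, "MODEL Endpoint = trtGroup symptom_at_baseline subgroup", adding the arm-by-subgroup interaction and listing both arm and subgroup as class variables. Its text does not itself promise odds ratios.

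The arm coding appears under primary safety (SAP 7.10.1.4): "Equals 1 if subject randomized to the treatment arm", and 0 for Control. The same section codes the safety event 1 for yes and 0 for no. SAP 7.9 codes both subgroup variables 0/1. The coding of `Endpoint` and `symptom_at_baseline` is not given in 7.10.7.

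**The concern.** Two SAS defaults matter. With no event option, PROC LOGISTIC models the first-ordered response level, which is absence under 1/0 coding. With no parameterisation option, a two-level class variable is effect-coded +1/-1 rather than 0/1. The text asks for odds ratios for presence, so the code and the text describe different quantities.

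At stake is the direction of one promised estimate in the main model: having the symptom at baseline would look protective against having it at 6 months. Also at stake is whether the subgroup model yields any readable arm effect. The code would be run for seven symptoms (SAP 7.10.7.3) and, across two subgroup sets, for 7 × 2 = 14 subgroup models. Ancillary programs receive peer review rather than independent programming (SAP section 8), so inherited sample code is less likely to be caught.

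**Working it through.** The plan gives no figure for this objective, so there is nothing to reproduce. The check is algebra on the code, then a numerical confirmation.

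**Inputs.** Arm: 1 = Treatment, 0 = Control (SAP 7.10.1.4). Subgroup: 0/1 (SAP 7.9). Assumed: `Endpoint` and `symptom_at_baseline` coded 1 = present, 0 = absent, following the SAP's event convention elsewhere. Also assumed, as software behaviour not stated in the documents: the first-ordered response level is modelled, and class variables are effect-coded with the last level as reference. Hence Control is x = +1 and Treatment is x = -1.

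**Main model.** The code fits logit P(absent) = a + b·x + c·base.

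- Log odds of presence are the negative of this. Treatment minus Control is -(a - b) + (a + b) = 2b, so the treatment odds ratio for presence is exp(2b). The column requested by `expb` shows exp(b), its square root: √0.30 = 0.55.
- The default odds-ratio table compares arm 0 with arm 1 for absence, which is also exp(2b). The reversed outcome and the reversed arms cancel, so the number is the intended treatment odds ratio.
- The baseline odds ratio for presence is exp(-c). Both the `expb` column and the default table show exp(c), its inverse: 1/4.0 = 0.25.

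**Subgroup model.** Add d·z + e·x·z, with z = +1 for subgroup 0 and -1 for subgroup 1. The log odds ratio for presence is 2b + 2e in subgroup 0 and 2b - 2e in subgroup 1.

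- The difference is 4e, so exp(e) = (OR in subgroup 0 / OR in subgroup 1)^(1/4). With 0.20 and 0.80: 0.25^(1/4) = 0.71.
- The sum is 4b, so the arm entry is exp(b) = (0.20 × 0.80)^(1/4) = 0.63, the square root of the geometric mean of the two odds ratios (0.40).
- Because the arm is in an interaction, the default table omits it. The `expb` column carries no interval.

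**Numerical check.** SAS was not available, so its defaults were emulated on simulated data.

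| Quantity | n = 70 | n = 20,000 |
|---|---|---|
| Intended treatment OR | 0.1228 | 0.4102 |
| `expb` column, arm | 0.3505 | 0.6405 |
| Default table, arm (0 vs 1, absence) | 0.1228 | 0.4102 |
| Intended baseline OR | 4.900 | 3.0619 |
| Baseline, both outputs | 0.2041 | 0.3266 |

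At n = 70 the default-table interval for the arm, 0.039 to 0.390, equals the intended one. The p-values (0.0004 for arm, 0.0079 for baseline) are the same in both fits. The simulated values are illustrative; the root and inverse relations hold in any data set.

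**Sensitivity to coding.** If presence sorts first (for example 1 = yes, 2 = no) and baseline is 0/1, the baseline odds ratio is right. The `expb` arm entry becomes 1/√OR (2.853 at n = 70), and the default table shows Control versus Treatment (8.140 = 1/0.1228).

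**The case against.** The strongest reply is that the promised results are odds ratios with intervals, and the `expb` column has no interval, so nobody following the text would report it. The default odds-ratio table from the same code already gives the right treatment estimate and interval. This stands. A reader might infer that the reported treatment effect would be shrunk toward 1, or that all the promised odds ratios would be wrong. The documents do not support that: nothing in 7.10.7.4 says to report the exponentiated coefficient, and for the main-model arm comparison, which is the purpose of the objective, the default table is numerically correct.

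Second, the code is offered only as similar to what may be used, the text is clear about the intended response, and the text should govern. This also stands, and lowers the weight of the point without removing the mismatch.

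Third, the coding of the symptom variables is assumed. This is true, so the inversion is conditional. But the omission is itself part of the problem, because the direction of the output depends on it.

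Fourth, baseline symptom is only an adjustment covariate, its inverted value is a valid odds ratio for absence, and 7.10.7.6 promises no odds ratios. The subgroup part of this stands as a limit: SAP 7.9 asks for assessment of the interaction term, and that p-value is unaffected. The baseline part does not fully answer the point, because 7.10.7.4 promises an odds ratio for every covariate in a model for presence.

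**Conclusion.** The sample code and the text disagree, and the consequence is narrow. Under 1 = present, 0 = absent coding and standard SAS defaults:

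- the baseline-symptom odds ratio is inverted in every output;
- the main-model treatment odds ratio and interval in the default table are numerically right, though labelled 0 versus 1 for absence;
- the `expb` column shows the square root of the treatment odds ratio;
- the subgroup model gives no arm odds ratio in the default table, and its `expb` interaction entry is the fourth root of the ratio of odds ratios (subgroup 0 over subgroup 1), without an interval.

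No p-value changes, and no primary or secondary result is touched. Severity is low: the objective is ancillary, with no hypothesis and no performance criterion, and the code is illustrative. The conclusion rests on the assumed symptom coding and on SAS defaults that were emulated rather than run.

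**What to change.** In SAP 7.10.7, state that `Endpoint` and `symptom_at_baseline` are coded 1 = present, 0 = absent.

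- Main model (7.10.7.4): use `CLASS trtGroup (REF='0') / PARAM=REF;` and `MODEL Endpoint(EVENT='1') = ...;` with the right-hand side unchanged. Drop `expb`, and say that odds ratios and intervals are taken from the odds-ratio table.
- Subgroup model (7.10.7.6): use `CLASS trtGroup (REF='0') subgroup (REF='0') / PARAM=REF;`, the same event option, no `expb`, and add `ODDSRATIO trtGroup / DIFF=REF;` to give the Treatment-versus-Control odds ratio and interval in each subgroup.

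With event and reference levels set this way, the n = 70 check returns the intended values directly: treatment 0.1228 (0.039 to 0.390) and baseline 4.900. The cost is a wording change to the SAP's sample code. Data collection, design and sample size are unaffected.

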7.10.7.5. Datasets Analyzed

The mITT analysis set, excluding subjects without the 6-month visit, will be used for this objective.

7.10.7.6. Subgroup Analyses

The subgroups to be analyzed are defined in section 7.9. A logistic regression model will be constructed each subgroup. The model will include covariates for subgroup and the interaction between subgroup and treatment.

Code similar to the following can be used for the logistic regression models:

```
PROC LOGISTIC DATA = Data;
  CLASS trtGroup subgroup;
  MODEL Endpoint = trtGroup symptom_at_baseline subgroup
    trtGroup*subgroup / expb;
  RUN;
```

7.10.8. Ancillary #5: Freedom from chronic treatment failure and off Class I and III anti-arrhythmic drugs following the blanking period

Compare the rate of chronic treatment success (primary effectiveness endpoint) between study arms for subjects off of Class I and III anti-arrhythmic drugs following the blanking period.

7.10.8.1. Hypothesis

There is no pre-specified hypothesis for this objective.

7.10.8.2. Performance Criteria and Rationale

There are no performance criteria for this objective.

7.10.8.3. Endpoint Definition

The endpoint for this objective is the primary effectiveness endpoint, chronic treatment success, as defined in section 7.10.2.3.

7.10.8.4. Analysis Methods

Kaplan-Meier curves will be used to estimate the rate of freedom from chronic treatment failure for each study arm. The Kaplan-Meier curves use the time that each subject is free from chronic treatment failure, defined from the date of procedure to the date of chronic treatment failure, if it occurs, or latest of the following: a) the last follow-up visit date, or b) the last date on which AF was assessed, if chronic treatment failure does not occur during the subject's study follow-up. Subjects will be included through all available study follow-up. A log-rank test will be used to determine if the freedom from chronic treatment failure rate differs between arms. An alpha of 0.05 will be used to determine statistical significance of the log-rank test.

Cox proportional hazards regression will be used to estimate the hazard ratio and its 95% confidence interval between study arms.

7.10.8.5. Datasets Analyzed

The following subjects will be included in this analysis:

- All subjects in the mITT analysis set that do not undergo an additional pulmonary vein ablation procedure during the 90 day blanked follow-up period will be included this analysis

AND

- Have not used Class I and III anti-arrhythmic drugs following the blanking period

Data from the Other Medication Log CRF will be used to determine if subjects have or have not used Class I and III anti-arrhythmic drugs following the blanking period. The log collects medication names which are classified as Class I or Class III anti-arrhythmic, etc. (SAS variable C_NAME). If a subject has not used Class I or III anti-arrhythmic drugs at all following the blanking period, all of their follow-up will be used for this analysis. If a subject has used either Class I or Class III anti-arrhythmic drugs after the blanking period, they will be excluded for this analysis.

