### 12.2 General considerations

A modified intention-to-treat analysis will be performed and will serve as the primary analysis for all objectives in this study. The modified intention-to-treat

cohort will include all randomized subjects that undergo a pulmonary vein isolation procedure (i.e. have a cryocatheter inserted). Patients that are randomized, and meet either of the following two conditions will not be included in this cohort:

- exit the study without undergoing a pulmonary vein isolation procedure
- subjects who are randomized to the treatment group and are found not to meet inclusion/exclusion criteria during the renal denervation procedure.

The Statistical Analysis Plan (SAP) will include a comprehensive description of the statistical methods and reports to be included in the final study report. Any change to the data analysis methods described in the CIP will require an amendment only if it changes a principal feature of the protocol. Any other change to the data analysis methods described in the protocol, and the justification for making the change, will be described in the clinical study report.

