## 12.6 Ancillary objectives

The ancillary objective endpoints below will be compared between study arms in order to further characterize the differences in outcomes between patients randomized to pulmonary vein isolation only to those randomized to pulmonary vein isolation and renal artery denervation. Mean, standard deviation, median, and range will be used as descriptive statistics for continuous variables and counts and proportions for categorical variables. An ANCOVA model will be used to compare the mean change in continuous variables from baseline to 6 months

between the study arms. The ANCOVA model will include change measurement (e.g. heart rate, blood pressure) from baseline to the 6-month follow-up visit as the response and study arm indicator and baseline measurement as covariates. For the symptoms ancillary objective, a logistic regression model will model presence of each symptom at 6 months as the response and study arm indicator and baseline presence of symptom as covariates. For the freedom from chronic treatment failure off anti-arrhythmic drugs objective, a log-rank test over all available follow-up will be performed. For the AF burden objective, the Mann-Whitney U test will be used to compare the AF burden between study arms. This non-parametric test is used rather than the Student's t-test since AF burden tends to have a skew distribution with many values near zero. The difference in AF burden will be characterized by the Hodges-Lehmann estimator, the median of all pairwise differences in AF burden between study arms.

- Office systolic and diastolic blood pressure at 6 months compared to baseline
- Heart rate at 6 months compared to baseline
- Procedural measures (total procedure time, cryoablation procedure time, renal artery denervation procedure time, ablation time, fluoroscopy time, dye usage)
- Symptoms at 6 months compared to baseline
- Freedom from chronic treatment failure and off Class I and III anti-arrhythmic drugs following the blanking period
- AF burden (percent of time in AF) over all follow-up after the blanking period

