Case Report Form (CRF) data will be used to determine if subjects have or have not used Class I and III anti-arrhythmic drugs following the blanking period. If a subject has not used Class I anti-arrhythmic drugs and has not used Class III anti-arrhythmic drugs at all following the blanking period, then they will be used for this analysis. If a subject has used either Class I or Class III anti-arrhythmic drugs after the blanking period, then they will be excluded from this analysis.

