7.13. Changes to Planned Analysis

Any change to the data analysis methods described in the CIP will require an amendment only if it changes a principal feature of the protocol. Any other change to the data analysis methods described in the CIP or this SAP, and the justification for making the change, will be described in the clinical study report.

The CIP states 'all randomized subjects will be included in the analysis' of some objectives (e.g., CIP section 12.4.5). This differs from CIP section 12.2 that states the mITT analysis set will serve as the primary analysis for all study objectives. The analysis sets for each objective as stated in this SAP will be used for the final report analyses.

8. Validation Requirements

Minimum validation requirements for the programs written to execute the analyses in this SAP:

- Primary objectives: Level I (independent program)
- Secondary objective: Level II (peer review)
- Ancillary objectives: Level II (peer review)

- AE tables and listings: Level II (peer review)
- Deviation table and listing: Level II (peer review)
- CONSORT diagram numbers: Level II (peer review)
- Other programs needed for final report analyses not specified: Level II (peer review)

Programs previously validated at Level I or Level II further modified with minor changes may be validated at Level III.

It is expected that Standard Operating Procedures will be followed for other programs that effect the programs written to execute the analyses in this SAP, such as data retrieval programs, dataset mapping programs, analysis dataset programs, etc.

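### Ancillary objective 5 names a joint outcome (free of treatment failure and off Class I/III drugs), but the SAP scores the primary endpoint alone in a subset selected on post-randomisation drug use

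*SAP*

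**What the plan says.** Protocol 12.6 lists the objective as "Freedom from chronic treatment failure and off Class I and III anti-arrhythmic drugs following the blanking period", and SAP section 4 repeats it. Protocol 12.2 says that the modified intention-to-treat analysis "will serve as the primary analysis for all objectives in this study".

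The SAP then sets out something different:

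- The opening of SAP 7.10.8 restates the aim as comparing chronic treatment success "for subjects off of Class I and III anti-arrhythmic drugs following the blanking period".
- SAP 7.10.8.3 fixes the outcome: "The endpoint for this objective is the primary effectiveness endpoint, chronic treatment success, as defined in section 7.10.2.3". Drug use is not a component.
- SAP 7.10.8.5 applies the filter: "If a subject has used either Class I or Class III anti-arrhythmic drugs after the blanking period, they will be excluded for this analysis". SAP 7.1.3 gives the same rule: "If a subject has used either Class I or Class III anti-arrhythmic drugs after the blanking period, then they will be excluded from this analysis".
- Both SAP sections also remove anyone who had a further pulmonary vein ablation in the 90-day blanking period. The protocol makes that restriction for the secondary objective (12.5.1 and 12.5.5) and not in 12.6.
- SAP 7.10.8.4 specifies Kaplan-Meier curves, a log-rank test at alpha 0.05 and a Cox model over all available follow-up.

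SAP 7.13 settles which rule is used: "The analysis sets for each objective as stated in this SAP will be used for the final report analyses". The discrepancy it discusses is all randomised subjects against mITT. It gives no reason for either filter.

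**The concern.** Under the joint outcome, a subject who starts a Class I or III drug after blanking has not achieved the endpoint. Under the SAP that subject is not in the analysis at all. Someone whose AF recurs in month 4 and who is then given a drug is deleted, and the recurrence goes too. The filter looks at the whole of follow-up, for which protocol Table 6 already lists windows to 42 months, so a late prescription removes earlier data.

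Such use can be expected, because protocol 6.7 only recommends being off antiarrhythmic drugs by day 90. If drugs are restarted because AF has returned, failures are removed selectively. The log-rank test then compares what remains of each arm after selection on a post-randomisation response, and the result is reported under the name of the joint outcome.

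**Working it through.** **The plan's own figures.** Ancillary objective 5 has no stated event count, power or expected drug-use rate. The nearest figures belong to the primary endpoint, and they reproduce: ln(0.75)/ln(0.50) = 0.415, and the three looks give 17.6% + 10.1% + 50.9% = 78.6% power. No design figure is in dispute.

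**Inputs.** Failure-free probability p is 50% in Control and 75% in Treatment, the planning rates in SAP section 6. Two inputs are assumed: r0, the share of failure-free subjects who use a Class I/III drug after blanking, and r1, the same share among failures.

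**Formulas** (drug filter alone, complete follow-up, no censoring):

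- Joint rate J = p(1 − r0)
- Share off drug D = p(1 − r0) + (1 − p)(1 − r1)
- SAP rate = J / D

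D is below 1 as soon as one subject uses a drug. Over full follow-up the SAP rate then exceeds J whenever J is above zero, whatever r0 and r1 are.

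**Numbers.** For r0 = 5% and r1 = 30%:

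- Control: J = 0.50 × 0.95 = 0.475; D = 0.475 + 0.50 × 0.70 = 0.825; SAP rate = 0.475/0.825 = 57.6%.
- Treatment: J = 0.75 × 0.95 = 0.7125; D = 0.7125 + 0.25 × 0.70 = 0.8875; SAP rate = 80.3%.

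| r0 | r1 | Joint, Control / Treatment | SAP rule, Control / Treatment | Excess in points |
|---|---|---|---|---|
| 0% | 10% | 50.0 / 75.0% | 52.6 / 76.9% | 2.6 / 1.9 |
| 5% | 30% | 47.5 / 71.3% | 57.6 / 80.3% | 10.1 / 9.0 |
| 5% | 50% | 47.5 / 71.3% | 65.5 / 85.1% | 18.0 / 13.8 |
| 5% | 70% | 47.5 / 71.3% | 76.0 / 90.5% | 28.5 / 19.2 |

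**In counts, 35 per arm (assumed).** Control has 17 recurrences (8 on drug) and 18 failure-free (2 on drug). The joint rate is 16/35 = 45.7%, the SAP rate 16/25 = 64.0% and the plain failure-free rate 18/35 = 51.4%. Treatment has 9 recurrences (4 on drug) and 26 failure-free (2 on drug). The three rates are 24/35 = 68.6%, 24/29 = 82.8% and 26/35 = 74.3%. A true joint rate can never exceed the plain rate; here the SAP figure does so in both arms, and 8 + 4 = 12 drug-treated recurrences leave the analysis.

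**Where the direction can reverse.** Take 35 subjects: 9 fail by 6 months and never use a drug, and 10 failure-free subjects start one after 6 months. The joint estimate at 6 months is 26/35 = 74.3%. The SAP rule gives 16/25 = 64.0%, because the later users are removed from the start.

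**Between arms.** With r0 = 0 and r1 = 50%, the difference shrinks from 25 to 19 points. With r0 = 20% and r1 = 10%, it grows from 20 to about 26. Scale matters as well. At r0 = 5%, moving from the joint outcome to the SAP rule at r1 = 30% and then 70% takes the absolute gap from 23.8 points to 22.7 and 14.5. The hazard ratio implied by ln(success in Treatment)/ln(success in Control) moves from about 0.455 to 0.40 and 0.36.

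**The case against.** The SAP is open about its question: it says the comparison is among subjects off drug and names the primary endpoint. The running text of protocol 12.6 also describes the objective more loosely than the list does, without the joining word, and gives no event definition. Reading it as a joint outcome is therefore partly interpretation. It remains the better reading, because the listed objective joins the two conditions, SAP section 4 repeats it, and the protocol states a subset explicitly where it wants one, in 12.5.5.

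The size is also open to challenge. Drug-use rates are assumed, 50% and 75% are 6-month planning rates while the filter covers all follow-up, and the formula has no time axis although the analysis is Kaplan-Meier. All of that stands, so the figures are illustrative.

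The consequences are limited. The objective is ancillary, with no hypothesis or performance criterion. The primary analysis applies neither filter, so drug-treated failures still count there.

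Three stronger readings are tempting and are not supported:

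- That success is always overstated in both arms. This holds against the joint outcome over full follow-up, but not for every fixed-time estimate. Against the plain success rate it needs r1 to exceed r0.
- That the treatment effect is inflated. The direction is not determined.
- That this rate is meant to inform a pivotal design. The protocol says so of the primary effectiveness rates (12.4.2) and the safety rates (12.3.3), not of this objective.

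**Conclusion.** The point holds as a mismatch between the named outcome and the planned analysis. Followed as written, SAP 7.1.3 and 7.10.8.5 estimate success in a set selected on a post-randomisation response. This is a wrong rule rather than a missing detail, because SAP 7.13 confirms that these sets will be used.

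For the drug filter alone over full follow-up, the reported rate exceeds the joint rate in any arm with at least one drug user and joint success above zero. With 5% drug use in non-failures and 30% to 70% in failures, the excess is about 10 to 28 points in Control and 9 to 19 in Treatment. With 0% and 10% it is about 2 to 3 points. The documents do not say where in this range the trial would fall. The re-ablation filter is a further unexplained departure and is not in these figures.

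**What to change.** In SAP 7.1.3 and 7.10.8:

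- Analyse all mITT subjects.
- Define the event as the earlier of chronic treatment failure and first Class I or III use after day 90. Use that continues past day 90 counts at day 91.
- Remove the re-ablation exclusion from this objective.
- Keep the drug-free subset only as a labelled descriptive or sensitivity analysis.
- Report the two event components separately by arm.

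The cost is SAP wording and one derived date. Protocol 6.7 already collects medication start and stop dates, so no new data are needed. Reported success will usually be less favourable.

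There is one real downside. Protocol 6.9 blinds subjects and centre staff only until after the pulmonary vein isolation procedure, and stopping drugs is only recommended, so open-label prescribing becomes part of the endpoint. Reporting the components separately lets a reader see how much of any difference comes from prescribing. The change is to an analysis rule only and does not touch drug management.
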